POTENTIAL RISKS ASSOCIATED WITH COMPREHENSIVE® SHOULDER SYSTEM WITH NANO HUMERAL COMPONENT IN TOTAL SHOULDER REPLACEMENT

The safety and efficacy of the Comprehensive[®] Shoulder System with nano humeral component has not been demonstrated clinically, and patients participating in the study may be subject to increased risks and/or adverse events, in addition to those listed under general surgical risks, including, but not limited to:

• Failure of biologic fixation resulting in loosening or migration of the implant

Risks/Benefits from the Investigational Device

All of the risks associated with the use of the nano humeral component are the same as those described for a total shoulder replacement arthroplasty. Given the stemless design of the nano humeral component, there may be an increased level in some of the implant-related risks, particularly for failure of biologic fixation resulting in loosening or migration of the implant. Loosening or migration could affect the implant position resulting in an unsatisfactory surgical outcome. Additional surgery would be required to replace the implant with an alternate prosthesis if excessive loosening or migration of the nano humeral component occurs.

Use of the nano humeral component prosthesis may benefit patients by reducing the amount of bone removed during the surgical procedure. In addition the nano humeral component does not violate the canal of the humerus. The amount of retained native bone is greater than for stemmed shoulder prostheses and could facilitate surgery for replacement of the nano humeral component with a micro or mini stem. Traditionally if a standard sized stem needs to be revised or removed, a "long" stem is used to replace it which results in a further violation of the canal and removal of bone. Leaving the canal intact allows the shaft of the humerus greater flexibility in adjusting to forces applied to it.

MINIMIZATION OF RISK

With the increased understanding of failure modes for total shoulders, pre-clinical testing and clinical results found in the literature, it is believed that none of the previously mentioned adverse events will occur in significantly higher numbers compared to the control device. This investigational plan has reduced the potential risk to the patient through the following methods:

- 1. By defining a patient population that limits the exposure of the device to patients conforming to the proposed indications, exclusions, and age requirements
- 2. By utilizing surgeon investigators who are licensed orthopedic surgeons that have significant experience with primary total shoulder arthroplasty, thereby reducing surgical related risk.
- 3. Developing a surgical technique, including instrumentation specifically designed for the investigational device that may help eliminate potential operative difficulties

Prior to deciding whether to participate in the investigation, each subject will be provided with a description of all potential complications and increased risks. Patients will also be provided with a description of alternate treatments. With this information and the counsel of their physician, patients will decide whether participation in the investigation and potential use of the investigational device is in their best interest. The provision of this information and the patients' consent to participate in the investigation will be documented through the use of an Informed Subject Consent form.

Only licensed orthopedic surgeons who are practiced in total shoulder replacement surgical procedures will be allowed to participate as clinical investigators for this investigation. General surgical risks will be controlled by surgeon adherence to accepted surgical guidelines and procedures. Risks related to the prosthetic design will be controlled by device labeling, and the investigators' adherence to the instructions for its safe handling and use.

The sponsor will further minimize the identified and/or emergent risks throughout the investigation by requiring the clinical investigators to document and report all complications and adverse effects to the investigation sponsor. Any unanticipated adverse device events will be reported to each clinical investigator, reviewing Institutional Review Board (IRB) and to the FDA. Based upon an evaluation of such events, the sponsor may either amend the investigational plan or terminate the investigation to protect the rights, safety and welfare of the subjects. Should an IRB decide to suspend or withdraw its approval for a clinical investigational subjects, the investigation sponsor will notify all reviewing IRBs, clinical investigators and the FDA of this action. To further minimize risks, any new information obtained during the course

of the investigation relating to risks to the patient will be provided to subjects, investigators, and IRBs.

The investigation has been designed to minimize the number of patients exposed to the investigational device, yet provide sufficient numbers of subjects for valid scientific analysis of the compiled investigation data. The risks will be further controlled by the investigational design, the procedures for monitoring the dispensing of the investigational devices to the investigation subjects and the documentation, reporting, and evaluation of the results from its surgical use.

The potential risks to the subjects in this investigation have been further minimized by the preclinical and laboratory testing performed by the sponsor to verify the design requirements and the suitability for the intended use. Use of the investigational device is further supported by the reports from the medical and scientific literature for similar devices and the manufacturing processes and controls used to manufacture the prosthesis.

Description of Subject Population

Condition

As stated in the investigational plan, subjects must meet specific diagnostic and inclusion/exclusion criteria to be eligible for enrollment. Eligible subjects will be selected for recruitment into the investigation from the general population of patients presenting with non-inflammatory degenerative joint disease (NIDJD). Subject candidates at increased surgical risk due to specific existing medical conditions are excluded as stipulated in the investigational plan. The relevant medical history and overall condition of each subject will be recorded and evaluated in relation to the safety and efficacy of the investigational device. This will enable the sponsor to identify additional contraindications, adverse effects, existing conditions and concurrent treatments that may predispose the subject to increased risk for complications or device failure.

Number

A total of 132 investigational devices and 132 control devices will be entered, providing a total investigation size of 264 devices.

Age

Subjects younger than 21 years or older than 90 years of age at the time of surgery are excluded from the investigation. In accordance with general orthopaedic and total joint replacement guidelines, skeletally immature subject candidates will be excluded from investigation participation. Data concerning the age of each investigational subject will be collected and evaluated to identify any age-related contraindications, or complications associated with the investigational device.

Gender

There is no gender selection criteria prescribed for this investigation. Male and female subject candidates will be solicited for participation in the investigation without bias. The proportion of male to female subjects will be examined to assure that there is no difference between control and investigational groups with respect to this ratio. If an unexpected difference in this ratio exists between control and investigational groups, then a covariate analysis controlling for gender will be performed for the primary analysis of the investigation. This will assure that gender related effects, if they are present, do not bias investigation conclusions.

Conclusion

This clinical investigation will be conducted under a well-defined protocol and subjects will be informed of the potential risks, benefits, and alternate treatments available prior to giving their consent for participation as investigational subjects. Exposure to the investigational device will be determined at random. Subjects' clinical course will be closely monitored and reported on throughout the investigation and new information provided to them that could affect their willingness to participate. The investigational device that will still allow for a valid, scientific analysis of the reported data. The reporting and assessment of all untoward events arising during the course of the investigation will also be required. Therefore, the sponsor believes that all risks that are reasonably foreseeable have been identified and the means for adequately controlling those risks described.

SECTION D: DEVICE DESCRIPTION DEVICE DESIGN AND DESCRIPTION

The Comprehensive[®] Shoulder System with nano humeral component is a humeral prosthesis system intended for use in shoulder replacement surgery. The implant can be utilized for primary shoulder replacement in conjunction with the 510(k) cleared Versa-Dial[™] Humeral Heads (K040610, K060716) and Comprehensive[®] Hybrid Glenoids (K060694). A complete component listing is included in Exhibit 12.

INVESTIGATIONAL DEVICE DESCRIPTION

The subject of this clinical investigation is the Comprehensive[®] Shoulder System with nano humeral component, comprised of the following components:

- A porous-coated stemless humeral component for cementless fixation;
- A polished, modular (2-piece) humeral head for articulation with the glenoid component;
- A molded glenoid component with three peripheral pegs for cemented fixation;
- Regenerex central glenoid peg for cementless fixation

Humeral Components

• The stemless humeral component is manufactured from Ti6Al4V alloy. It consists of a central tapered region and six outer wings. The taper has a machine finish and accepts the taper adaptor of the humeral head component. A small groove is included just

below the taper to accept an inserter/impactor. The bonecontacting outer surface features a porous coating of plasma-sprayed titanium alloy for cementless fixation in the proximal humerus. Six sizes are available – 30 mm, 32 mm, 34 mm, 36 mm, 38 mm, and 40 mm, as referenced to

the outside diameter.

• The head component consists of two parts: a humeral head and a taper adaptor. The humeral head is manufactured from CoCrMo alloy, while the taper adapter is made from Ti6Al4V alloy. The convex portion of the head is highly polished for smooth articulation against the glenoid component. The two

piece construct allows the offset to be adjusted from 0.5 mm to 4.5 mm and then oriented in any direction to maximize coverage of the resected humerus.

Glenoid Components

- The glenoid component consists of two parts: a glenoid base and a central peg.
- The glenoid base is manufactured from ultra-high molecular weight polyethylene. The base has three ribbed peripheral pegs that allow for cemented fixation in the glenoid.
- The central peg is manufactured from porous metal that is sintered over a solid Ti6Al4V alloy core. The porous metal of the central peg allows for cementless fixation of this portion of the glenoid component.

CONTROL DEVICE DESCRIPTION

The Comprehensive® Shoulder System with mini stem component, which will be the control device for this clinical investigation and was 510(k) cleared under K060692 on May 30, 2006, comprises the following components:

- Proximally porous-coated humeral stem for cementless fixation;
- Polished, modular (2-piece) humeral head for articulation with the glenoid component;
- Molded glenoid component with three peripheral pegs for cemented fixation;
- Regenerex central glenoid peg for cementless fixation

Humeral Component

• The humeral stem component is manufactured from Ti64AlV alloy. The taper has a machine finish and accepts the taper adaptor of the humeral head component. The proximal region of the bone-contacting outer surface features a porous coating of plasma-sprayed titanium alloy, while the distal portion is polished.

Seventeen stem diameters are available – 4 mm to 20 mm, in 1-mm increments.

• The humeral head components are identical to those described in the Investigational Device Description section.

Glenoid Components

• The glenoid component is identical to those described in the Investigational Device Description section.

SECTION E: MONITORING

The Investigator must allow regular inspection of all study records including CRFs, source documents and regulatory documents during the study by the monitor or other representatives of the sponsor. This measure is to ensure that the study is carried out and documented in accordance with federal regulations and the terms of this protocol. The Investigator also agrees to allow inspections by the FDA or their agents or other regulatory agencies before, during, or after the study has concluded, if such inspections are requested.

The monitor for this study will be the Clinical Operations Department of the Sponsor located at: Biomet Manufacturing, Inc [name]

Monitoring may also be conducted by consultants contracted by and acting on the behalf of the sponsor not known at this time. Regardless, monitoring will be conducted according to the most current version of the sponsor's business unit procedure and corporate procedure regarding monitoring. Samples of the sponsor's monitoring procedures are included in Exhibit 6.

SECTION F: LABELING PACKAGE LABEL

Samples of the outer package label for the investigational Comprehensive[®] Shoulder System with nano humeral component are contained in Exhibit 7.

INSTRUCTIONS FOR USE (IFU)

A sample of the package insert (IFU) for the Comprehensive[®] Shoulder System with nano humeral component is contained in Exhibit 8.

SURGICAL TECHNIQUE

The surgical technique for the Comprehensive[®] Shoulder System with nano humeral component is contained in Exhibit 9. A list of the instrumentation to be used for implantation of the investigational device is contained in Exhibit 10.

NOTE: A recommended rehabilitation protocol from Brigham and Women's Hospital has been provided in Exhibit 13. All patients are required to participate in a rehabilitation protocol as prescribed by their surgeon. Any patient that does not participate will be considered a protocol deviation.

SECTION G: CONSENT MATERIALS

A copy of the proposed informed consent for the study is contained in Exhibit 5.

SECTION H: IRB INFORMATION

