The study is designed as a prospective, multi-center, randomized, single blinded, controlled study. Patients will be enrolled at a maximum of seventeen (17) centers. Patients will be evaluated pre-operatively and at 6 weeks, 3 months, 1 year, 2 years and annually thereafter until the last patient entered into this study has completed their 2-year evaluation.

STUDY GROUPS AND TREATMENTS

Patients will be randomized to either the Comprehensive® Shoulder System with nano humeral component (investigational) or the Comprehensive® Shoulder System with mini stem component (control) group. Patients will be randomized using a 1:1 (Investigational: Control) blocked randomization plan. The treatment assignment will be revealed intraoperatively. Every attempt will be made to blind patients to their treatment until the end of the study. If a patient is revised or withdraws consent and at the request of the patient, blinding may be discontinued as no further data will be collected.

NUMBER OF PROCEDURES

A total of 264 subjects will be enrolled in this study (132 Control and 132 Investigational).

SELECTION OF SUBJECTS

All subjects considered for participation in the study will be assessed according to predetermined eligibility criteria, listed below. All subjects considered for enrollment must be

recorded on the Subject Screening Log (see Exhibit 11), including patients who are considered but not consented, consented but not randomized and consented and randomized.

Inclusion Criteria

- Patients with non-inflammatory degenerative joint disease including osteoarthritis.
- Patients where the device will be used in the correction of a functional deformity, specifically deformities that prevent congruent articulation of the glenohumeral joint. Examples include but are not limited to: humeral head structural deformity, osteophyte formation restricting range of motion, etc.
- Patients with pain and/or loss of function in the shoulder for whom other treatment modalities have been unsuccessful. Examples include but are not limited to: activity modification, physiotherapy, and anti-inflammatory or other types of medication.
- Patients requiring unilateral or staged bilateral shoulder arthroplasty

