- Patient must be anatomically and structurally suited to receive the implants. During the pre-operative templating, it must be confirmed that the humeral neck is of sufficient diameter to implant at least the smallest nano humeral component and that the humeral neck cortex is intact.
- Patients who are 21-90 years of age at the time of surgery.
- Patients who are skeletally mature
- Patients with an ASES score \leq 40.
- Patients who are willing and able to return for scheduled follow-up evaluations
- Patients who have completed a valid, IRB approved Informed Consent Form
- Patients for whom the surgeon has confirmed intraoperatively has no cyst > 1cm and not more than one cyst at the implantation site
- Patients who agree to be blinded to treatment until evaluations are completed at the 22+ month endpoint.

Exclusion Criteria

- Patients diagnosed with avascular necrosis or post-traumatic arthritis of the humeral head
- Patient presents with shoulder joint infection, sepsis, osteomyelitis or distant foci of infections which may spread to the implant site.
- Patients with cuff tear arthropathy.

- Patients who have undergone a Hemi-, Total, or Reverse Total Shoulder arthroplasty in the affected shoulder.
- Patient presents with a malunion or non-union of the tuberosities of the proximal humerus.
- Patients with osteoporosis, osteomalacia, rheumatoid arthritis, metabolic disorders of bone, muscle or connective tissue, gross deformity or any other condition of the proximal humerus (defined as severe destruction or deformity of the proximal humerus that precludes placement of the device) that in the Investigator's medical judgment could compromise implant fixation or bone healing.
- Rapid bone destruction, marked bone loss or bone resorption apparent on roentgenogram.
- Patients with neurologic or other disorders that would either affect the stability of the shoulder prosthesis, i.e., Charcot's joint, uncontrolled seizures, etc.
- Patients diagnosed with any condition that may limit their ability to complete the consent form or would affect their capability or willingness to return to the clinic for assessments and/or follow directions (i.e. mental illness).
- Bone cancer, either primary or secondary, that affects the shoulder.
- Patients presents with symptoms of chronic steroid use as defined as use of oral steroids for a chronic condition for 12 months prior to and including the date of surgery (inhaled and topical steroid usage is allowed).

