Missing Data: Patients who refuse to return for follow-up or who cannot be located and/or do not formally withdraw consent are described as "missing data." Sites will be instructed to continue efforts to contact these patients. See Statistical Plan for more information on how missing data will be handled in the analysis.

Osteolysis: As defined in Exhibit 3: Radiographic Protocol.

Other Interventions: This category includes other surgeries the patient incurs while enrolled in the study that are seemingly unrelated to the implanted device. This would include surgeries such as cholecystectomy, appendectomy, coronary artery bypass surgery, etc.

Revision: A procedure that removes part of the original implant configuration, with or without replacement of the entire component configuration.

Removal: A procedure where the entire original system configuration is removed.

Reoperation: Any surgical procedure that does not include removal or revision, for example, drainage of a hematoma at the surgical site.

Screen Failure: A patient who is either screened but not consented, consented but not randomized or randomized but does not receive the investigational or control device.

Adverse Event (AE): Any event occurring in a study subject that, in the opinion of an M.D. or other qualified and trained medical professional, represents an untoward medical occurrence that differs in either nature, severity, or frequency from a normal post-operative finding. AEs may not have an apparent causal relationship with the device. An AE can therefore be any discrete or ongoing unfavorable and unintended sign (including an abnormal laboratory finding), symptom, or disease temporally associated with the use of a product.

Serious Adverse Event: Any untoward medical occurrence that:

- Results in death
- Is life-threatening
- Requires in-patient hospitalization* or prolongation of existing hospitalization
- Results in persistent or significant disability/incapacity
- Results in congenital anomaly/birth defect

*A planned hospitalization for a pre-existing condition, or a procedure required by the protocol, without a serious deterioration in health is not considered to be a serious adverse event.

Unanticipated Adverse Device Event: any serious adverse event that is or may possibly be related to the device other than those listed in Section C: Risk Analysis or in the institution's approved Informed Consent.

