A significant disability is one that causes substantial disruption to the person's normal life and activity.

The investigator or designee must complete the SAE reporting (SAE100). Then relative to the event, a Revision/Removal Form (RR 100), and/or the Withdrawal Form (WD100) form should be completed. See the Implant Retrieval and Analysis of Removed Implants section below for instructions on how to handle investigational devices that are removed from study subjects.

DISCONTINUATIONS AND REVISIONS (SUBJECT WITHDRAWAL)

It is recognized that the subject's participation in this trial is entirely voluntary, and that she/he may refuse to participate and may withdraw from participation at any time without jeopardy to any future medical care. Device Revision or Removal is also considered a withdrawal event when all components are removed, or if only the humeral stem is removed. No additional study follow-up is necessary. In the event that a patient receives a partial revision (not all components/humeral stem), a revision/removal form should be completed, but the patient should still be followed per protocol. Do not complete a withdrawal form for these patients. *Enrollment for this study is defined as receipt of either a control or an investigational device.*

Therefore:

- Subjects withdrawn from the study after receipt of either the control or investigational device will NOT be replaced.
- Randomized patients who do not ultimately receive the control or investigational device:
 - 1. *WILL* be replaced, but
 - 2. Randomization assignment will not be re-used
- *All* subject withdrawals must be documented on the Withdrawal Form (WD100).

- Includes randomized patients who do not ultimately receive the control or investigational device configurations.
- If withdrawal is due to device removal or revision, the SAE 100 form must be completed. The Revision/Removal form (RR 100) should be completed in all cases including device removal details, if known.

Copies of all Case Report Forms are included in Exhibit 4.

CONTROL OF INVESTIGATIONAL DEVICE

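### The unblinding permission covers every revised patient, yet partially revised patients stay in follow-up and can give later ASES and SANE scores unblinded

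*Combined protocol and SAP*

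**What the plan says.** Section B, Study Groups and Treatments, sets the aim for blinding: "Every attempt will be made to blind patients to their treatment until the end of the study". It then gives an exception. The blind may be lifted when a patient "is revised or withdraws consent and at the request of the patient, blinding may be discontinued as no further data will be collected". The exception draws no line between full and partial revision.

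Study Definitions and Glossary of Abbreviations defines a revision as "A procedure that removes part of the original implant configuration, with or without replacement of the entire component configuration". Partial revisions are therefore revisions. The glossary's entry for withdrawal is narrower: apart from death and written withdrawal of consent, it covers only removal of all components or of the humeral stem components.

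Discontinuations and Revisions (Subject Withdrawal) agrees with that narrower entry: "Device Revision or Removal is also considered a withdrawal event when all components are removed, or if only the humeral stem is removed". For any other revision, "a revision/removal form should be completed, but the patient should still be followed per protocol". Sites are also told: "Do not complete a withdrawal form for these patients".

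Three other places bear on the same patients:

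- The closing list under Secondary Endpoints gives revision/removal as a reason for discontinuation, with no exception for partial revision.
- Subject Accounting subtracts revised subjects from the number expected at a visit, again with no exception.
- Missing Data and Sensitivity Analyses asks for an ASES score before the revision where possible, but does not say that this score replaces one taken later at 22+ months.

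**The concern.** Treatment assignment is revealed during surgery, so the surgeon knows the implant. The trial is single-blinded, and the patient's own blinding is what protects scores that patients report. The SAP discusses ASES among patient-reported measures, and ASES at 22+ months is one of three co-primary endpoints.

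The exception permits unblinding on the ground that data collection has stopped. For a partially revised patient it has not. A site can follow both sections to the letter and still collect ASES and SANE from a patient who knows which device was implanted and has just had part of it removed. Unblinding cannot be undone. If partial revision is more frequent in one arm, any resulting bias in the scores would also differ by arm.

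**Working it through.** **The sections side by side**

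1. The unblinding permission is triggered by revision, without qualification (Study Groups and Treatments).
2. Revision includes removal of part of the implant (glossary).
3. Revision ends follow-up only if all components or the humeral stem are removed (glossary entry for withdrawal; Discontinuations and Revisions).
4. Patients who meet 2 but not 3 stay in follow-up, which includes ASES and SANE at every postoperative visit (Table 1, Screening and Follow-Up Clinical and Radiographic Exams).
5. The Analysis Population admits subjects with complete 22+ month data for a primary endpoint, and subjects revised or removed at or before 26 months. A partially revised patient with a 22+ month ASES can qualify on either ground.

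So the permission reaches patients for whom its stated reason does not hold. Nothing in the SAP clearly keeps their later scores out of the primary ASES analysis.

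**Check of the plan's ASES figures**

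Inputs from Sample Size Calculation: SD 19, margin 9.5, one-sided α 0.05, power 90%, 1:1 allocation.

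- Normal approximation: n = 2 × (1.645 + 1.282)² × (19/9.5)² = 68.5, so 69 per arm.
- Exact t-test: power is 0.8993 at 69 and 0.9030 at 70, so 70 per arm, as stated.
- Attrition: 70/0.85 = 82.4, so 83 per arm, as stated.

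The concern changes none of these figures.

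**Size of the exposure**

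The revision rate of 2.0% comes from the sample size section for Absence of Revision/Removal/UADE. Enrolment is 132 per arm.

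- Revised shoulders: 0.02 × 132 = 2.64 per arm; 0.02 × 264 = 5.28 in total.
- This is an upper limit at that rate. Only partial revisions count, and only where the patient asks to be unblinded before the 22+ month score. The documents do not give that share. If 25% to 100% is assumed, the total is 1.3 to 5.3 patients.

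**Effect on the ASES mean**

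The shift in an arm mean is the proportion affected times the shift per score. The shift per score is an assumption.

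- At 5 to 10 points per score, all revised shoulders affected, one arm only: 0.02 × 5 = 0.10 and 0.02 × 10 = 0.20 points. That is about 1% to 2% of the 9.5-point margin.
- For comparison, the standard error of the difference is 19 × √(2/112) = 2.54 points with 112 per arm, and 19 × √(2/132) = 2.34 with 132 per arm.
- Extreme case, 19 points (one full SD) on every revised shoulder in one arm: 0.02 × 19 = 0.38 points, or 4% of the margin. With 132 per arm, a shift against the device lowers ASES power from 0.992 to 0.988. A shift in its favour raises the one-sided type I error of the ASES test from 0.050 to 1 − Φ(1.645 − 0.38/2.34) ≈ 0.069.

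**The case against.** **The permission limits itself.** It is optional, needs a request from the patient, and gives the end of data collection as its reason. A careful site might apply it only to revisions that end follow-up. This stands in part: a reader might infer that revised patients will be unblinded as a matter of course, and the text does not say so. But the trigger word is revision, the glossary gives it a wide meaning, and the reason is stated as a fact about revised patients rather than as a condition to check.

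**Other sections support the permission.** The discontinuation list under Secondary Endpoints and the expected count in Subject Accounting both treat revision as ending participation. The request for a pre-revision ASES could mean that this earlier score is the one analysed, and it would precede any unblinding under the revision rule. This also stands in part. A reader might infer that unblinded scores from these patients certainly enter the co-primary analysis; the documents leave that open. They do not settle it the other way either, and the explicit instruction to sites is to continue follow-up.

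**The end of blinding.** A reader might also see a contradiction between blinding to the end of the study and the inclusion criterion "Patients who agree to be blinded to treatment until evaluations are completed at the 22+ month endpoint". The documents do not support that. The criterion is the least a patient must agree to, and the longer period is a best effort. Both can hold.

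**The effect is negligible.** This is largely right. A shift of 0.5 points in an arm mean would need 5% of the arm unblinded (0.05 × 10), and the documents give no such revision rate. A revised shoulder also already fails the revision co-primary and, if revised before two years, the radiographic one. Success requires all three endpoints.

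**Conclusion.** The text is wrong as written, and the point is minor. The permission to unblind rests on a reason that the protocol's own follow-up rule makes untrue for partially revised patients. They can give ASES and SANE scores unblinded, possibly including the 22+ month ASES.

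The expected effect is about 0.1 to 0.2 points on one arm's mean ASES. That assumes the plan's 2% revision rate, that every revision is partial and unblinded in time, that only one arm is affected, and a 5 to 10 point shift per score. The first comes from the documents. The next two push the figure up, and the size of the shift is not in the documents. This is a defect of consistency and conduct. The documents do not support reading it as a threat to the sample size or the ASES margin. It is worth correcting because the correction is nearly free and unblinding is irreversible.

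**What to change.** 1. In Study Groups and Treatments, limit the permission. Suggested wording: *A patient may be told which implant was used, on request, only once data collection has ended, that is, after written withdrawal of consent or after a revision or removal that counts as a withdrawal under Discontinuations and Revisions. Patients with any other revision stay blinded while study scores are still being collected.*
2. Record the date of any unblinding on the case report form.
3. Reconcile the discontinuation list under Secondary Endpoints, Missing Data and Sensitivity Analyses, and the expected count in Subject Accounting with Discontinuations and Revisions. They should agree on whether partially revised patients remain in follow-up.
4. State in the SAP whether the pre-revision or the 22+ month ASES enters the primary analysis for these patients.

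An analysis that drops scores given after unblinding is not recommended. It would remove failed shoulders selectively, which could flatter the arm with more failures, and with roughly 0 to 3 patients per arm it would tell little.

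The cost is protocol and SAP wording plus one date field; sample size, margin and primary test are unchanged. The downside is that a few partially revised patients wait longer to learn their implant, and one who objects could withdraw consent and contribute no later scores.
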